3.1 Overall Study Design

This is a four-visit multi-center, randomized, double-masked, parallel-group study evaluating the safety and efficacy of CSF-1 compared with Vehicle in approximately 300 subjects with presbyopia. The study design is summarized in Figure 1.

Visit 1 (Screening, Day -14 to -1): Qualified subjects will receive 1 drop of Vehicle instilled in each eye, followed by preliminary efficacy assessments to identify Vehicle responders at 15 minutes post-vehicle instillation.

Vehicle responder is defined as a subject who had a > 0.14 LogMAR (i.e., 7 letters) improvement in post-Vehicle treatment (at 15 minutes post-Vehicle treatment) monocular BDCVA in either eye at 40 cm

compared to Visit 1 pre-treatment, or a > 0.14 LogMAR (i.e., 7 letters) improvement in monocular BDCVA in either eye at 40 cm between Visit 1 (pre-treatment) and Visit 2 (pre-treatment baseline).

Visit 2 (Day 1): Baseline assessments. Subjects who meet all inclusion and none of the exclusion criteria and qualify as Vehicle non-responders, will be randomized 1:1 to one of the following treatment arms:

- CSF-1 (0.4% pilocarpine hydrochloride ophthalmic solution)
- Vehicle

Pre-treatment measurements taken at this visit are considered as baseline.

[figure not shown]
At the Visit 2 (Day 1) clinic visit, study personnel will instill Dose 1 of study drug at 8:30 AM \pm 30 minutes in each eye. Efficacy and safety assessments will be conducted for 2 hours following Dose 1. Dose 2 will be instilled by study personnel at 10:30 AM \pm 30 minutes in each eye. Efficacy and safety assessments will be conducted for 4 hours following Dose 2.

All subjects will be instructed to dose twice daily (BID) with a single drop in each eye for approximately 1 week. The first daily dose should occur in the morning, with the second dose following 2 hours later (± 1 hour). Subjects will be instructed not to dose at home on clinic visit days.

Visit 3 (Day 8): Study personnel will instill Dose 1 of study drug at 8:30 AM \pm 30 minutes in each eye. Efficacy and safety assessments will be conducted for 2 hours following Dose 1. Dose 2 will be instilled by study personnel at 10:30 AM \pm 30 minutes in each eye. Efficacy and safety assessments will be conducted for 2 hours following Dose 2.

[figure not shown]

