4.1 Method of Assigning Subjects to Treatment Groups

Each subject who signs an informed consent form (ICF) will be assigned a subject number. Subject numbers will be assigned in sequential order beginning with 001. Once a subject meets all qualification criteria at Visit 2 (Day 1), they will be randomized in a 1:1 ratio via an Interactive Response Technology (IRT) system to one of the following treatment groups: (1) CSF-1 or (2) Vehicle, and stratified by iris color (brown versus light [i.e., blue, green, gray, and hazel]) and by baseline manifest refraction spherical equivalent <-0.5 D, -0.5 D to +0.75 D, and >+0.75 D); randomization will not be stratified by site.

At least, approximately, 30% of subjects will have a light iris and at least, approximately, 30% will have a brown iris. The actual percentages will vary based on enrollment.

Randomization will be used to avoid bias in the assignment of subjects to treatment, to increase the likelihood that known and unknown subject attributes (e.g., iris color and baseline characteristics) are evenly balanced across treatment groups, and to enhance the validity of statistical comparisons across treatment groups. Double-masked treatment will be used to reduce the potential of bias during data collection and the evaluation of clinical endpoints.

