4.2 Masking and Unmasking

An independent, unmasked biostatistician who is not otherwise involved in the trial will generate the complete randomized study drug kit list. The subject, study sponsor, medical investigators, and study staff will be masked during the entire randomization process and throughout the course of the study. When medically necessary, the investigator may need to determine what treatment has been assigned to a particular subject. When possible (i.e., in non-emergent situations), [REDACTED] and/or the study sponsor should be notified before unmasking the IP. In emergency situations, the investigator must notify the sponsor within 24 hours after determining that it is necessary to unmask the treatment assignment. The investigator must also indicate in source documents and in the electronic case report form (eCRF) that the mask was broken and provide the date, time, and reason for breaking the mask.

5. Sample Size and Power Considerations

A total sample size of 280 subjects (140 subjects per arm) yields > 97.5% power to establish superiority of CSF-1 to Vehicle in the percentage of study eyes demonstrating a \geq 3-line (15-letter) gain from baseline in BDCVA at 40 cm (Precision Vision chart) and no loss of BDCVA \geq 5 letters (ETDRS at 4 m), 1-hour post

each dose on Visit 3 (Day 8) assuming a response rate of 42.5% in CSF-1 and 17.5% in Vehicle using a Pearson chi-squared test with a 2-sided significance level of 0.05.

A series of horizontal black bars of varying lengths, likely representing redacted text or data. The bars are arranged vertically and span the width of the page. Some bars are longer, while others are shorter, indicating different lengths of redacted content.

Accounting for approximately a 5% discontinuation rate, approximately 150 subjects per arm (approximately 300 total) will be randomized.

6. Data Preparation

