8.4 Data Analysis Conventions

All data analysis will be performed by SDC after the study is completed and the database has been locked and released for unmasking. Statistical programming and analyses will be performed using SAS® Version 9.4 or higher. Output will be provided in rich text format for tables and portable document format for tables, listings, and figures using landscape orientation. All study data will be listed by subject, treatment, and visit (as applicable) based on all randomized subjects unless otherwise specified.

Summaries for continuous and ordinal variables will include the number of observations, arithmetic mean, standard deviation (SD), median, minimum, and maximum. Minima and maxima will be reported with the same precision as the raw values; means and medians will be presented to 1 additional decimal place than reported in the raw values. Standard deviations will be presented to 2 additional decimal places than reported in the raw values. Summaries for discrete variables will include frequency counts and percentages. All percentages will be rounded to 1 decimal place (i.e., XX.X%). Change from baseline will be calculated as baseline subtracted from the relevant post-baseline visit (Post-Baseline Visit – Baseline Visit), with baseline defined in Section 8.3 of this SAP.

Gains or improvements in BDCVA at 40 cm (Precision Vision chart) of \geq 3-lines (15-letters) are defined as changes from baseline in BDCVA at 40 cm (Precision Vision chart) of \leq -0.30 logMAR (e.g., -0.30, -0.32, ... logMAR).

Gains or improvements in BDCVA at 40 cm (Precision Vision chart) of \geq 2-line (10-letters) are defined as changes from baseline in BDCVA at 40 cm (Precision Vision chart) of \leq -0.20 logMAR (e.g., -0.20, -0.22, ... logMAR).

[figure not shown]
Similarly, loss in BDCVA of \geq 5 letters (ETDRS at 4 m) are defined as changes from baseline in BDCVA (ETDRS at 4 m) of \geq 0.10 logMAR (e.g., 0.10, 0.12, ... logMAR).

All statistical tests, unless otherwise indicated, will be 2-sided with a significance level of 0.05 ($\alpha = 0.05$). Confidence intervals (CI) for differences between treatment groups will be 2-sided at 95% confidence. All p-values will be rounded to 4 decimal places; p-values less than 0.0001 will be presented as " <0.0001 "; p-values greater than 0.9999 will be presented as " >0.9999 ." Unless otherwise specified, summaries will be presented by treatment group and, where appropriate, visit.

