12.1 Primary and Key Secondary Efficacy Analysis

The primary efficacy endpoint in this study is the percentage of subjects with a ≥ 3 -line (15-letter) gain, from baseline, in best distance-corrected visual acuity (BDCVA) at 40 cm (Precision Vision chart) and no loss in BDCVA ≥ 5 letters (ETDRS chart) at Visit 3, 1 hour following Dose 1 in the study eye. The key secondary efficacy endpoints are defined the same as the primary efficacy endpoint, except for being measured at 2 hours following Dose 1, 1 hour following Dose 2, and 2 hours following Dose 2, all at Visit 3.

The primary and key secondary efficacy analysis will be conducted in the FAS with missing data handled in the following manners:

1. Discontinuation of study drug and non-optimal compliance will be ignored [treatment policy strategy].
2. Withdrawal due to lack of efficacy or AEs: missing data will be singly imputed as failure [hypothetical strategy].
3. Missing data without withdrawal or withdrawal due to reasons other than lack of efficacy or AEs: missing data will be imputed employing Multiple Imputation (MI) using randomized treatment-based Markov Chain Monte Carlo (MCMC) methods.

No subject data will be excluded from the FAS due to protocol violations/deviations. The multiple imputation of missing values will be completed for the continuous measures (BDCVA at 40 cm and BDCVA at 4 m), then the response variable will be determined therefrom. Imputation of failure due to lack of efficacy or AE will be assigned after multiple imputation is performed.

Variables for treatment group, baseline for BDCVA at 40 cm and baseline for BDCVA at 4 m will also be included in the multiple imputation model. 25 complete imputed datasets will be created.

Example SAS® code for the multiple imputation:

```
PROC MI DATA=DATAIN OUT=MI NIMPUTE=25 SEED=118787 minimum=-0.3 maximum=1;
  MCMC INITIAL=EM;
  VAR TRTPN VA40 VA40BL VA4 VA4BL;
RUN;
```

Where TRTPN = treatment group, coded 1 for CSF-1, else 0

VA40 = value of BDCVA at 40 cm for Visit 3, 1 hour after Dose 1

VA40BL = baseline value of BDCVA at 40 cm

VA4 = value of BDCVA at 4 m for Visit 3, 1 hour after Dose 1

VA4BL = baseline value of BDCVA at 4 m

For each imputed dataset, a logistic regression model with baseline BDCVA at 40 cm as a covariate and treatment as a main effect will be used to obtain the treatment effect estimate, odds ratio, and 95% confidence interval (CI) for odds ratio.

Example SAS® code for the logistic model is shown here:

```

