PROC LOGISTIC DATA=MI DESCENDING OUTTEST=PARMS COVOUT;
  BY _IMPUTATION_;
  CLASS TRTP;
  MODEL AVALC = BASE TRTP;
RUN;
```

where

- TRTP is the treatment arm (CSF-1, Vehicle);
- BASE is the baseline of BDCVA (letters) at 40 cm in the study eye;
- AVALC is the indicator for efficacy variable (Y, N).

SAS® PROC MIANALYZE will be used to obtain the overall p-value, odds ratio, and 95% confidence interval (CI) for odds ratio.

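### The efficacy models could also adjust for two pre-randomisation acuity readings already collected, for a small gain in test power

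*SAP*

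**What the plan says.** SAP 12.1 fits the same model to the primary endpoint and the three key secondary endpoints: "a logistic regression model with baseline BDCVA at 40 cm as a covariate and treatment as a main effect will be used". The example code is "MODEL AVALC = BASE TRTP", where BASE is the study eye's 40 cm baseline. SAP 12.2 uses this model again for sensitivity analyses 1 to 3 and for the tipping-point analysis. The mixed model in Protocol 10.7 also carries the 40 cm baseline as its only baseline acuity.

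Two other pre-randomisation readings exist:

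- **4 m baseline.** SAP 8.4 defines the no-loss component as a change from it. SAP 12.1 uses it for imputation: "baseline for BDCVA at 40 cm and baseline for BDCVA at 4 m will also be included in the multiple imputation model".
- **Visit 1 pre-treatment 40 cm reading.** The Vehicle-responder rule in SAP 3.1 needs it. One limb of that rule looks for a more than 7-letter "improvement in monocular BDCVA in either eye at 40 cm between Visit 1 (pre-treatment) and Visit 2 (pre-treatment baseline". Under SAP 8.3 this reading serves as baseline only when the Visit 2 value is missing.

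**The concern.** The endpoint is built from two change scores, each counted from a single baseline reading. An eye that reads poorly at 40 cm by chance at Visit 2 is more likely to show a 15-letter gain later. Given the Visit 2 value, the Visit 1 reading helps to separate true near acuity from that day's reading error, so it carries information about the outcome that BASE alone does not. In the same way, an eye that reads well at 4 m by chance at baseline is more likely to show a 5-letter loss.

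Both readings precede randomisation, so adjusting for them cannot introduce post-treatment bias. At stake is a little test power on four hypotheses tested in strict order (SAP 8.5), where a miss at one step stops the rest.

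**Working it through.** **Inputs from the documents**

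- SAP section 5: "A total sample size of 280 subjects (140 subjects per arm) yields > 97.5% power to establish superiority of CSF-1 to Vehicle", "assuming a response rate of 42.5% in CSF-1 and 17.5% in Vehicle using a Pearson chi-squared test with a 2-sided significance level of 0.05". About 300 are to be randomised, allowing for 5% discontinuation.
- SAP 4.1: "they will be randomized in a 1:1 ratio via an Interactive Response Technology (IRT) system".
- SAP 8.4: "All statistical tests, unless otherwise indicated, will be 2-sided with a significance level of 0.05". Also, 15 letters = 0.30 logMAR, so 1 letter = 0.02 logMAR.
- Between-subject SDs, reading error and correlations are not given. Those used below are assumptions.

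**Step 1. Reproduce the planning figure.** With p1 = 0.425, p2 = 0.175, mean 0.30 and n = 140 per arm:

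power = Φ{[p1 − p2 − 1.96√(2 × 0.30 × 0.70/n)] / √[(p1(1 − p1) + p2(1 − p2))/n]}
= Φ{[0.25 − 1.96 × 0.05477] / √(0.38875/140)}
= Φ(0.14265/0.05270) = Φ(2.707) = 0.9966.

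This agrees with the stated lower bound. For exactly 97.5% power, n = [1.96√0.42 + 1.96√0.38875]²/0.25² = 6.211/0.0625 = 99.4, or 100 per arm. For discontinuation, 140/0.95 = 147.4, or 148 per arm, consistent with about 150. The planning test has no covariates, so this power does not depend on adjustment.

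**Step 2. Size the gain.** Large-sample simulation, about 400,000 per arm, with reading error and the 0.14 logMAR Visit 1 to Visit 2 screen, calibrated to 42.5% v 17.5%. Relative efficiency (RE) = Wald chi-squared of the larger model / Wald chi-squared of the planned model. Power is scaled to 280 subjects.

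Base assumptions in logMAR: true near SD 0.10, near error 0.05, SD of drug response 0.12, true 4 m SD 0.07, 4 m error 0.04, near/4 m correlation 0.3. Ranges explored across all scenarios: 0.07-0.12, 0.03-0.10, 0.03-0.12, 0.03-0.07, 0.025-0.09 and 0.3-0.7 respectively.

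| Scenario | No 4 m loss (Vehicle/CSF-1) | RE, add 4 m | RE, add Visit 1 near | RE, add both | Power, planned to both |
|---|---|---|---|---|---|
| Base | 92/92% | 1.000 | 1.017 | 1.017 | 99.40 to 99.46% |
| Low error | 97/97% | 1.000 | 1.011 | 1.011 | 99.37 to 99.41% |
| High error | 84/84% | 1.001 | 1.025 | 1.028 | 99.50 to 99.58% |
| High error, small true variance | 84/84% | 1.003 | 1.019 | 1.023 | 99.61 to 99.67% |
| 4 m shift of 0.04 on CSF-1 | 92/78% | 1.002 | 1.014 | 1.017 | 99.39 to 99.46% |
| Correlation 0.7 | 84/84% | 1.000 | 1.024 | 1.025 | 99.50 to 99.58% |
| Deliberately extreme | 76/76% | 1.027 | 1.025 | 1.056 | 99.53 to 99.68% |

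The 4 m baseline adds little because most eyes pass the no-loss component.

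A second simulation used 1,200 trials of 300 subjects per setting, with near error 2.5-4.0 letters, 4 m error 2.0-3.5 letters, between-subject SDs of 8 letters (near) and 4 letters (4 m), and an SD of individual change of 7 letters. RE was 1.002-1.012 for the 4 m baseline, 1.013-1.020 for the Visit 1 near reading and 1.015-1.028 for both. In subjects, 0.015 × 300 = 4.5 and 0.028 × 300 = 8.4, so about 5 to 8.

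**Step 3. What happens to the odds ratio.** SE ratio = (log odds ratio with both / log odds ratio planned) / √RE.

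- Low error: (1.268/1.251)/√1.011 = 1.008
- Base: (1.291/1.263)/√1.017 = 1.014
- High error: (1.359/1.309)/√1.028 = 1.024

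The estimate moves away from zero by more than its SE grows. The test gains, but the interval on the log scale becomes slightly wider.

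**Step 4. A smaller effect, for illustration.** At an assumed 32.5% v 17.5% with 280 subjects, power goes from 82.1 to 82.7% (base), 83.3 to 84.4% (high error) or 84.0 to 85.9% (extreme).

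**The case against.** The strongest reply is that this is a preference and not a defect. In a randomised comparison the one-covariate model is valid and type I error is unaffected. The protocol likewise carries only the 40 cm baseline acuity, and no planned figure relies on further adjustment. All of that stands, and it is why the point is optional. The iris-colour and refraction strata are also outside the model, so the choice of covariates is a judgement. Nor can the plan be faulted for giving no reason: parts of Protocol 10.7 are redacted, and material in SAP sections 16 and 18 is not shown.

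The reply also shows that changing the MODEL line alone is not enough. The Visit 1 reading is not in the PROC MI variable list. If it entered only the analysis model, imputed outcomes would ignore it and its association with response would be diluted. PROC LOGISTIC drops records with a missing covariate. Where Visit 1 already replaces a missing Visit 2 baseline, the two near covariates would be identical. The fix below deals with these.

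Four stronger readings might be inferred, and the documents support none of them:

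- *The 4 m baseline is the serious omission because it defines half of the composite.* Alone it adds about 0-1% in plausible settings.
- *The omission widens the reported confidence interval, or leaves chance imbalance as bias.* Step 3 shows that the odds-ratio interval would not narrow. Chance imbalance is already allowed for in the test and interval.
- *The 2-hour tests suffer most.* No 2-hour response rate is visible, and text after the power statement is redacted. Step 4 is an illustration, not a statement about H02 or H04.
- *The imputation and analysis models contradict each other.* An imputation model may properly contain more variables than the analysis model.

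**Conclusion.** The omission is real and the direction is clear, but the effect is small. Adding both readings gives about 1-3% more test efficiency under plausible assumptions (5.6% in the extreme row of the table). Nearly all of the plausible gain comes from the Visit 1 near reading. At the planned rates this is 0.2 power point or less on H01, where the planning test already has about 99.7%. The gain lies in test power, or in the precision of a marginal risk difference such as Protocol 10.7 foresees. For the odds ratio that SAP 12.1 reports, the conditional estimate moves away from 1 and the SE of its logarithm rises by about 1-2%.

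Every size quoted rests on SDs and error terms that are not in the documents; masked Visit 1 and Visit 2 data could replace them. Priority: an optional, low-cost improvement.

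**What to change.** Before unmasking, amend SAP 12.1 and 12.2 as follows:

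1. Use `MODEL AVALC = BASE VA4BL VA40V1 TRTP`, where VA40V1 is the study eye's Visit 1 pre-treatment 40 cm reading. Apply it to H01 to H04, sensitivity analyses 1 to 3 and the tipping-point model.
2. Add VA40V1 to the PROC MI VAR list so that the imputation and analysis models agree.
3. State how VA40V1 is handled when it is missing, including in the analyses without multiple imputation, so that no subject drops out of a model. State also how it is handled when the Visit 1 value already serves as BASE.
4. State that the odds ratio is conditional on these three baselines.

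The cost is SAP wording, small changes to the imputation and model code, two degrees of freedom and a slightly different conditional odds ratio. No new data are needed. The change should not be made after unmasking, when a choice of covariates would no longer be credible.

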### 10.5 Sample Size

A total sample size of 280 subjects (140 subjects per arm) yields >97.5% power to establish superiority of CSF-1 to Vehicle in the percentage of study eyes demonstrating a  $\geq 3$ -line (15-letter) gain from baseline in BDCVA at 40 cm (Precision Vision chart) and no loss of best distance corrected VA  $\geq 5$  letters (ETDRS at 4m), 1-hour post each dose on Visit 3 (Day 8) assuming a response rate of 42.5% in CSF-1 and 17.5% in Vehicle using a Pearson chi-squared test with a 2-sided significance level of 0.05.

[REDACTED]

Accounting for approximately a 5% discontinuation rate, approximately 150 subjects per arm (approximately 300 total) will be randomized.

Estimates were obtained from the Phase 2 study (18-150-0006) Intent-to-Treat (ITT) population response for pilocarpine 0.4% vs. diclofenac (control), additionally imputing missing data as failures.

At least approximately 30% of subjects will have light (i.e., blue, green, gray, and hazel) iris, and at least approximately 30% will have a brown iris. The actual percentages will vary based on enrollment.

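### SAP 12.1: the treatment factor has no reference coding and no back-transformation is shown, so exponentiating the pooled coefficient would report the square root of the odds ratio

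*SAP*

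**What the plan says.** SAP section 12.1 covers the primary endpoint (Visit 3, 1 hour after Dose 1) and the key secondary endpoints at "2 hours following Dose 1, 1 hour following Dose 2, and 2 hours following Dose 2, all at Visit 3", so four endpoints in all.

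For each imputed dataset, a logistic model with baseline near acuity and treatment "will be used to obtain the treatment effect estimate, odds ratio, and 95% confidence interval (CI) for odds ratio". The code is introduced with the words "Example SAS® code for the logistic model is shown here". Its relevant lines are:

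- "PROC LOGISTIC DATA=MI DESCENDING OUTTEST=PARMS COVOUT", run by imputation;
- `CLASS TRTP;`, with no coding option, where TRTP has the two levels CSF-1 and Vehicle;
- "MODEL AVALC = BASE TRTP".

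Pooling is then covered by one sentence: "PROC MIANALYZE will be used to obtain the overall p-value, odds ratio, and 95% confidence interval (CI) for odds ratio". No MIANALYZE statements, input dataset or transformation are given.

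For the imputation step, the same section defines a numeric treatment variable, TRTPN, coded 1 for CSF-1 and 0 otherwise. The model code does not use it.

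**The concern.** PROC MIANALYZE combines the estimates and variances that it is given; it does not turn a coefficient into an odds ratio. Someone must exponentiate, and the result is an odds ratio only if the pooled coefficient is a full log odds ratio. With `CLASS TRTP;` and nothing more, PROC LOGISTIC codes a two-level factor as +1 and -1. The arms then differ by two units, and the coefficient is half the log odds ratio.

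The odds ratio and its interval are the only pooled comparative effect measures that section 12.1 names. Protocol section 10.7 also planned marginal proportions and a difference in proportions, but section 12.1 does not carry these over, and SAP section 1 says that its methods supersede the protocol's. If the scale is wrong, the headline effect estimate is wrong, and the p-value beside it gives no warning.

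**Working it through.** **Inputs**

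- Planning rates: "1-hour post each dose on Visit 3 (Day 8) assuming a response rate of 42.5% in CSF-1 and 17.5% in Vehicle" (Protocol 10.5; repeated in SAP 5). They are stated for the 1-hour assessments only. No 2-hour rates are visible, and text after the power statement is redacted.
- 140 evaluable subjects per arm, two-sided alpha 0.05 (same sections).
- Default CLASS coding in PROC LOGISTIC: effect coding, last level in sort order as reference, so CSF-1 = +1 and Vehicle = -1. This is general software knowledge and is treated as an assumption here.

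**1. The plan's own figure.** The documents state no odds ratio, so the check is on power. The pooled rate is 0.30.

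- Null SE = sqrt(2 × 0.30 × 0.70 / 140) = 0.0548.
- Alternative SE = sqrt((0.425 × 0.575 + 0.175 × 0.825) / 140) = 0.0527.
- Power = Φ((0.25 - 1.96 × 0.0548) / 0.0527) = Φ(2.71) = 0.9966, consistent with the stated >97.5%.

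**2. The coding.** Write logit(p) = a + b·BASE + c·x.

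- With x = 1 or 0, the difference between arms is c, so c = log OR.
- With x = +1 or -1, the difference is 2c, so c = log(OR)/2 and exp(c) = sqrt(OR).

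This does not depend on the response rates, so it applies to every endpoint run through the code.

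**3. Size at the 1-hour planning rates (unadjusted).**

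- OR = (0.425/0.575) / (0.175/0.825) = 3.484; log OR = 1.248; half of it = 0.624; exp(0.624) = 1.867.
- SE of log OR = sqrt(1/59.5 + 1/80.5 + 1/24.5 + 1/115.5) = 0.2805; half of it = 0.1403.

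| Quantity exponentiated | Estimate | 95% CI | Wald z |
|---|---|---|---|
| Full log OR | 3.48 | 2.01 to 6.04 | 4.45 |
| Effect-coded coefficient | 1.87 | 1.42 to 2.46 | 4.45 |

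**4. Check with a covariate.** One simulated dataset (150 per arm, assumed baseline covariate) was fitted both ways.

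- Reference coding: coefficient 0.927, SE 0.266, exponentiated 2.53.
- Effect coding: coefficient 0.464, SE 0.133, exponentiated 1.59, which is sqrt(2.53).
- The p-value is 0.00049 under both.

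**5. Pooling does not change this.** Halving the coefficient in all 25 imputations halves their mean and divides the within- and between-imputation variances by four. The pooled SE is halved and the ratio of the two variances is unchanged. The test statistic, degrees of freedom and p-value therefore stay the same.

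**6. The 2-hour endpoints.** Only assumed rates can be used. At 35% v 15% the pair is 3.05 and 1.75; at 25% v 15% it is 1.89 and 1.37.

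**The case against.** The strongest reply is that the wrong step is not in the SAP. The code is labelled an example, and the text asks for the odds ratio, so a programmer who reported its square root would be departing from the text. The per-imputation odds-ratio table is correct under either coding, and its logarithm and SE could be pooled instead. In our copy the output option reads `OUTTEST`, whereas the SAS option is `OUTEST`, which again points to illustrative text. The Tables section is empty in our copy, so any output specification there cannot be seen.

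Much of this stands. A reader might infer that the SAP commits the sponsor to reporting 1.87 in place of 3.48 for all four endpoints. The documents do not support that: no exponentiation is written out, and the planning rates cover only the two 1-hour endpoints. A reader might also infer that the trial's conclusion is at risk. It is not: success and the hierarchy rest on p-values that are the same under both codings, and a square root moves an odds ratio towards 1, so it cannot create a claim of benefit.

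It is also fair to say that the slip could be noticed. The first three sensitivity analyses in SAP 12.2 involve no pooling and can use PROC LOGISTIC's own odds-ratio output. Assuming 5% missing in each arm counted as failures, the 1-hour rates become 0.40375 and 0.16625 and the odds ratio is about 3.40. A primary value of 1.87 beside it would look odd.

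That does not remove the point. The one output that the example sends forward is coefficients with covariances, on the wrong scale for direct exponentiation. A gap between primary and sensitivity results could be misread as an effect of missing data.

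**Conclusion.** The point holds as a defect of specification. The example code sets up a half-scale treatment coefficient, sends it to pooling, and leaves out the step that would have to correct the scale. Anyone who follows the code and then exponentiates would report the square root of the odds ratio and of both confidence limits, for each of the four endpoints.

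The conclusion rests on the SAS default coding and on the usual next step being taken without doubling. The pair 3.48 and 1.87 is an unadjusted illustration for the 1-hour endpoints; only the square-root relation carries over to the 2-hour endpoints. The consequence is confined to the reported effect size and its interval. Because an interval excludes 1 exactly when its square root does, the misreported result would look consistent with its own p-value, which is why the coding should be settled in the plan.

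**What to change.** In the example code of SAP 12.1:

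1. Replace the CLASS line with `CLASS TRTP (REF='Vehicle') / PARAM=REF;`. Alternatively, drop CLASS and put the existing 0/1 variable TRTPN in the MODEL statement.
2. Correct `OUTTEST` to `OUTEST`.
3. Add the PROC MIANALYZE call, naming its input dataset and the treatment parameter. State that the pooled log odds ratio and its two limits are exponentiated to give the reported odds ratio and 95% CI.

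If effect coding is kept for any reason, the SAP should say that the pooled coefficient and its SE are doubled before exponentiation.

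The cost is a few lines of text and code. Sample size, data collection, the tests and the hierarchy are untouched.
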